The primary objective of this study is to identify dose(s) for further clinical study through the comparison of HbA1c change from baseline in each active group that will receive bexagliflozin tablets, 5 mg, 10 mg, or 20 mg, to the placebo group over 12 weeks of treatment.

Secondary Objectives:

- To assess the change in HbA1c over time
- To assess the efficacy of bexagliflozin tablets in lowering FPG as a function of time
- To assess the efficacy of bexagliflozin based on the proportion of subjects who reach the American Diabetes Association (ADA) and the Japan Diabetes Society target HbA1c of <7%
- To assess the effect of bexagliflozin on systolic and diastolic blood pressure over time
- To assess the effect of bexagliflozin on body weight over time
- To assess the safety of bexagliflozin in subjects with T2DM

Other endpoint:

Population pharmacokinetic evaluation of bexagliflozin plasma concentration

Study Design:

THR-1442-C-449 is a phase 2b multicenter, double-blind, placebo-controlled parallel group study to assess the effect of once daily bexagliflozin tablets on HbA1c in either treatment-naïve type 2 diabetic subjects or in subjects who have been treated with one oral anti-diabetic

agent. To be eligible, a prospective subject of either gender must have T2DM and an HbA1c value between 7% and 8.5% at the screening visit if treatment naïve or an HbA1c value between 6.5% and 8.5% if currently treated with one oral hypoglycemic agent and willing to undergo a 6 or 10 week washout.

All eligible subjects who are treatment naïve or who have completed the washout will start a 2 week placebo run-in period. Subjects who are deemed compliant in taking the run-in medication (*i.e.*, miss no more than one dose during the run-in period) and have HbA1c between 7 and 8.5% at the end of the run-in period will be eligible for randomization and will receive investigational product.

Approximately 320 subjects divided equally into 4 groups will be randomly assigned to take oral bexagliflozin tablets, 5 mg, 10 mg, 20 mg, or placebo, once daily for 12 weeks in an out-patient setting. Subjects with hyperglycemia based on fasting blood glucose levels may receive approved anti-diabetic medication.

Subjects will visit their study sites at weeks 2, 6, and 12 for safety and efficacy evaluation, with a follow-up visit at week 14.

Measurement of bexagliflozin plasma concentration over time (sparsely sampled) will also be conducted at 20 centers and will include approximately 240 study subjects as part of a bexagliflozin population PK study.

Study Population:

Approximately 320 diabetic subjects will be randomized.

Prospective subjects must be:

1. Men or women ≥ 20 years of age at screening. Women of childbearing potential must test negative by urine pregnancy test and agree to abstain from coitus or use contraception during the entire study period to avoid any possible pregnancy. Females who are surgically sterile (by reason of hysterectomy or oophorectomy) or postmenopausal (most recent menses more than 12 months prior to screening) are eligible if they test negative by urine pregnancy test.
2. Treatment naïve (*i.e.*, have never received prescription anti-diabetic medications or have received no more than 14 days of prescription medications for diabetes in the 12 weeks prior to enrollment) or currently taking one OHA in combination with diet and exercise
3. Diagnosed with T2DM with HbA1c levels at screening between 7.0% and 8.5% (inclusive) if treatment naïve or with HbA1c levels between 6.5 and 8.5% (inclusive) if on one oral anti-diabetic medication
4. Currently having a body mass index (BMI) ≤ 40 kg/m²
5. Taking stable doses of medication for hypertension or hyperlipidemia as determined by adherence to a regimen that has not changed for at least 30 days prior to screening (if

applicable)

6. Able to comprehend the study participation requirements and willing to provide written informed consent in accordance with institutional and regulatory guidelines
7. Able to maintain adequate glycemic control at the run-in visit (for subjects who complete the washout)
8. Having an HbA1c between 7.0 and 8.5% (inclusive) prior to randomization (day -3 to -5):
9. Capable of adhering to the investigational product administration requirements as evidenced by omission of no more than one dose of run-in medication

Test Product, Dose, and Mode of Administration:

Bexagliflozin tablets, 5, 10, 20 mg or placebo, once daily by mouth before breakfast

Duration of Treatment:

12 weeks

Efficacy Assessments:

Primary efficacy assessment:

- Change in HbA1c over 12 weeks of treatment

Secondary efficacy assessments:

- Change in HbA1c over time
- Proportion of subjects with HbA1c <7%
- Change in body weight over time
- Change in FPG over time
- Change in systolic and diastolic blood pressure over time

Samples for population PK analysis will be collected and the required plasma concentrations determined. The PK parameters will be assessed separately as part of the population PK analysis.

Safety Assessments:

Safety will be assessed based on an analysis of the adverse events record; of laboratory data, including hematology, serum chemistry, urinalysis, urinary electrolytes and creatinine; of electrocardiograms (ECGs), vital signs and physical examinations; and of concomitant medication use.

Statistical Methods:

Data summaries will use descriptive statistics (number of subjects [n], mean, standard deviation [SD], Q1, median, Q3, minimum, and maximum) for continuous variables, and frequency and percentage for categorical and ordinal variables. If there are missing values, the number missing will be presented, but without a percentage. All data collected will be included in by-subject data listings.

For the primary endpoint of HbA1c change from baseline over 12 weeks of treatment, a

mixed model repeated measures (MMRM) analysis of covariance model (ANCOVA) with baseline HbA1c as a covariate will be fitted on the available data, incorporating all visits at which HbA1c was measured from each subject including the scheduled visits at weeks 2, 6, and 12 as well as the unscheduled visits for measurement of HbA1c. Treatment, study center, and stratification factor for randomization (treatment naïve versus taking one OHA at baseline) will be applied as fixed effects, as will study week and study week-by-treatment interaction. From this model, an estimate of the treatment difference at week 12 will be generated, as will an assessment of whether this estimate is significantly different when comparing placebo with each dose of bexagliflozin at a two-sided 0.05 level of significance. An unstructured within-patient covariance structure will be assumed. HbA1c values obtained after the start of rescue medication will be excluded from this primary analysis.

The MMRM model is one approach to obtain treatment effect estimates in the presence of missing data. As sensitivity analyses for missing data, the following will be performed:

1. Missing HbA1c data (for weeks 2, 6, or 12) will be imputed via multiple imputation, following which the MMRM will be repeated on the complete datasets with results combined across complete datasets using standard MI techniques; HbA1c values collected after the start of rescue medication will be considered missing.
2. Missing HbA1c data will be imputed via LOCF, following which the MMRM will be repeated; HbA1c values collected after the start of rescue medication will be considered missing.
3. HbA1c values collected after the start of rescue medication will NOT be considered missing, and the MMRM analyses will be re-performed.

The effect of bexagliflozin on fasting blood glucose, blood pressure, body weight, change in HbA1c over time, and proportion of subjects who reach HbA1c < 7% will be evaluated as secondary endpoints. These endpoints are considered exploratory and will not be adjusted for multiplicity.

Safety and tolerability of bexagliflozin in subjects with T2DM will also be assessed descriptively. Data summaries will be produced for AEs, physical exam results, vital signs, ECG results, and clinical lab results including serum chemistry, hematology, serum lipids, glycemic control parameters and urinalysis.

Date of Original Approved Protocol: 29 September 2014

Date of Revised Protocol: 16 February 2015

LIST OF ABBREVIATIONS AND DEFINITIONS OF TERMS

ADA	American Diabetic Association
AE	Adverse event
ALT	Alanine aminotransferase
ALP	Alkaline phosphatase
ANCOVA	Analysis of covariance
ANOVA	Analysis of variance
AST	Aspartate aminotransferase
ATC	Anatomic therapeutic chemical
BMI	Body mass index
BUN	Blood urea nitrogen
CI	Confidence interval
CK	Creatinine kinase
CRF	Case report form
CRO	Contract research organization
CV	Cardiovascular
DPP4	Dipeptidyl peptidase 4
DSMB	Data and Safety Monitoring Board
ECG	Electrocardiogram
eGFR	Estimated glomerular filtration rate
FAS	Full analysis set
FPG	Fasting plasma glucose
γ -GTP	Gamma-glutamyl transferase
GCP	Good Clinical Practice
GLP-1	Glucagon-like peptide-1
h	Hour
HbA1c	Glycated hemoglobin
HBsAg	Hepatitis B surface antigen
Hct	Hematocrit
HCV	Hepatitis C virus
HDPE	High density polyethylene
HF	Heart failure
Hgb	Hemoglobin
HIPAA	Health Information Portability and Accountability Act
HIV	Human immunodeficiency virus
ICCR	In country caretaker representative
ICH	International Conference on Harmonisation
IEC	Independent Ethics Committee
IND	Investigational New Drug

IRAE	Immediately reportable adverse event
IRB	Institutional Review Board
ITT	Intent-to-treat
IWRS	Interactive web response system
LDH	Lactic dehydrogenase
MACE	Major adverse cardiovascular event
MDRD	Modification of diet in renal disease
MedDRA	Medical Dictionary for Regulatory Activities
MI	Myocardial infarction
MMRM	Mixed model repeated measures
MODY	Maturity-Onset Diabetes of the Young
NYHA	New York Heart Association
OHA	Oral hypoglycemic agent
PD	Pharmacodynamics
PK	Pharmacokinetics
SAE	Serious adverse event
SBP	Systolic blood pressure
SD	Standard deviation
SGLT2	Sodium glucose cotransporter 2
SMBG	Self-monitored blood glucose
SOP	Standard operating procedure
T2DM	Type 2 diabetes mellitus
TEAE	Treatment emergent adverse event
TIA	Transient ischemic attack
UACR	Urine albumin-to-creatinine ratio
UGE	Urinary glucose excretion
ULN	Upper limit of normal
UPT	Urine pregnancy test
UTI	Urinary tract infection
WOCBP	Woman of child bearing potential
WHO-DD	World Health Organization Drug Dictionary

1 INTRODUCTION

Type 2 diabetes mellitus (T2DM) is one of the leading causes of morbidity and mortality worldwide, affecting an estimated 387 million people in 2014 and reaching epidemic proportions in nearly all countries in the world. Approximately 179 million of those affected are estimated to be unaware of their condition and over 80% reside in low- and middle-income countries (International Diabetes Foundation, 2014). T2DM accounts for at least 90% of all diabetes cases. Despite the availability of several classes of therapeutics, the number of people with T2DM is projected to increase by 55% to over 590 million adults by 2035. Among the debilitating consequences of T2DM are peripheral neuropathy, retinopathy, renal failure, peripheral ischemia and exacerbations of cardiovascular disease, which result in blindness, amputation, dialysis and death.

T2DM is a disease of insulin resistance and is strongly linked to increased body fat mass in the majority of cases (Schwartz et al., 2012). Weight loss has been shown to improve glycemic control and to reduce the severity of diabetes-associated comorbidities, supporting the view that anti-diabetic agents that promote weight loss may be particularly beneficial for the treatment of the disease (Look et al., 2013; Scheen and Van Gaal, 2014).

Asian populations may be particularly at risk for the adverse consequences of increased body mass. Metabolic syndrome, a presentation of diabetes with comorbid hypertension and dyslipidemia, increases more rapidly with increasing weight among Asians than among non-Asians and it has been proposed that the BMI ranges that define the overweight and obese categories should be lower in Asian populations than in non-Asian populations (Palaniappan et al., 2011).

Several classes of agents are available for treating T2DM, including insulin and its secretagogues, PPAR γ agonists, biguanides, alpha glucosidase inhibitors, glucagon-like peptide 1 (GLP-1) receptor agonists and dipeptidyl peptidase 4 (DPP4) inhibitors. However, the rapid growth rate in the incidence of T2DM has led to an increasing recognition that additional therapeutics are needed to provide safe and effective reductions of elevated plasma glucose levels. New agents to treat T2DM will ideally reduce hyperglycemia and avoid common side effects of currently available agents, such as weight gain, gastrointestinal disturbances, and hypoglycemia.

The renal Na⁺/glucose transport protein SGLT2 actively transports extracellular glucose into cells using the driving energy of the transmembrane electrochemical potential for sodium ions. Individuals with disruptions in SLC5A2, the gene encoding SGLT2, exhibit prominent glucosuria in the absence of significant co-morbidities (Santer et al., 2003; van den Heuvel et al., 2002). The excretion of glucose in the urine of diabetic subjects in amounts comparable to or greater than that seen in individuals harboring loss of function mutations in SLC5A2 has the potential to improve both fasting and postprandial hyperglycemia without increasing insulin secretion, causing weight gain, or inducing hypoglycemia.

1.1 Bexagliflozin for the Treatment of Type 2 Diabetes Mellitus

Bexagliflozin (previously identified as EGT0001442), is a potent and highly specific inhibitor of the SGLT2 with an *in vitro* IC₅₀ of 2 nM or 0.9 ng/mL and a 2435-fold selectivity for human SGLT2 compared with SGLT1. Bexagliflozin elicits a prominent and predictable glucosuria in laboratory animals and human subjects.

1.1.1 Summary of Non-clinical Data with Bexagliflozin

The potential adverse effects of bexagliflozin have been evaluated in studies of non-clinical safety pharmacology, acute and chronic general toxicology, genotoxicity, acute and chronic reproductive toxicity and two-year carcinogenicity. Repeat dose toxicity studies have found exacerbation of chronic progressive nephropathy and gastric irritation, including sporadic ulceration, at the lowest observable dose level in male rats, as well as signs of reversible cardiac inflammation and abdominal distension at a dose level of 200 mg/kg in monkeys. Details of the adverse findings are provided in the Investigator's Brochure.

1.1.2 Summary of Clinical Data with Bexagliflozin

Theracos has completed eight phase 1 studies to evaluate safety, tolerability, pharmacokinetics (PK), pharmacodynamics (PD) and drug metabolism in healthy subjects, subjects with T2DM, and diabetic subjects with renal impairment. Details of the pharmacology, efficacy, and safety assessments are described in the Investigator's Brochure and summarized in the following sections.

Bexagliflozin exhibits high permeability and is a weak Pgp substrate and inhibitor. It produces dose-proportional exposures in humans and animals. Metabolism in humans is most similar to that in monkeys, and the principal pathway for biotransformation in humans is glucuronide formation. The majority of bexagliflozin and related metabolites are excreted within 48 to 72 h in humans, rats and monkeys, and there is no evidence of accumulation. Bexagliflozin is neither a significant inducer nor inhibitor of cytochrome P450 isozymes relevant for drug-drug interactions.

In the course of bexagliflozin therapeutic development, several formulations have been evaluated. Immediate release capsule formulations have been used in the initial clinical pharmacology and phase 2 studies. A program to develop an extended release tablet formulation that would reduce daily variation in the concentration of the compound was carried out and resulted in the identification of a mucoadhesive formulation with the desired properties. The drug products exhibit a greater than 75% release of drug substance by 8 h in simulated gastric fluid *in vitro*.

2 STUDY OBJECTIVES

2.1 Primary Objective

The primary objective of this study is to identify the optimal dose(s) through the comparison of mean HbA1c change in subjects who receive bexagliflozin tablets, 5 mg, 10 mg, 20 mg, or placebo, after 12 weeks of treatment.

2.2 Secondary Objectives

The secondary objectives of this study are the following:

- To assess the change in HbA1c over time
- To assess the efficacy of bexagliflozin tablets in lowering fasting plasma glucose (FPG) over time
- To assess the efficacy of bexagliflozin based on the proportion of subjects who reach the American Diabetes Association (ADA) and the Japan Diabetes Society target HbA1c of <7%
- To assess the effect of bexagliflozin on systolic and diastolic blood pressure over time
- To assess the effect of bexagliflozin on body weight over time
- To assess the safety of bexagliflozin in subjects with T2DM

Other exploratory objective includes:

- Population pharmacokinetic evaluation of bexagliflozin plasma concentration

3 INVESTIGATIONAL PLAN

3.1 Overall Study Design and Plan

THR-1442-C-449 is a phase 2b multicenter, double-blind, placebo-controlled, dose range finding study to assess the efficacy and safety of once daily bexagliflozin in either treatment-naïve type 2 diabetic subjects or subjects previously treated with one oral hypoglycemic agent (OHA). The primary efficacy endpoint will be placebo-adjusted reduction in HbA1c, measured after 12 weeks of treatment. Treatment naïve subjects are those who have never received prescription anti-diabetic medications or who have received no more than 14 days of prescription medications for diabetes in the 12 weeks prior to enrollment. The study will enroll men and women with T2DM and with HbA1c between 7% and 8.5% (inclusive) at the screening visit (for subjects who are treatment naïve) or with T2DM and with HbA1c between 6.5% and 8.5% (inclusive) at screening visit (for subjects who have received one OHA and who are willing and able to undergo a washout period.)

Approximately 400 subjects who meet all the inclusion criteria, none of the exclusion criteria, and who consent to participate in the study are eligible to be enrolled to complete a 6 to 10 week washout if needed and a 2 week placebo run-in period prior to being randomized. Subjects who can adhere to the run-in medication dosing schedule (i.e., miss no more than one dosage in 2 weeks) and who have HbA1c between 7 and 8.5% at baseline (visit S5) will be eligible for randomization and receive investigational product. A 20% screen fail rate is expected by the end of run-in, leading to approximately 320 subjects eligible for randomization to receive oral bexagliflozin tablets, 5, 10, 20 mg or placebo once daily for 12 weeks in an outpatient setting. Subjects who experience hyperglycemia during the study may receive approved anti-diabetic medication. Subjects will visit their study site at weeks 2, 6, and 12 for safety and efficacy evaluation, with a follow up visit at week 14.

Measurement of bexagliflozin plasma concentration over time (sparsely sampled) will be conducted at 20 centers and will include approximately 240 subjects who consent to participate the PK study. Three samples from each subject will be drawn at weeks 2, 6, or 12.

3.2 Research Methods and Procedures

3.2.1 Washout and Run-in Period

Eligible subjects who are not treatment naïve will discontinue their current OHA and enter a 6- or 10-week washout. Those who are taking any OHA except a thiazolidinedione will discontinue the medication for 6 weeks. Subjects who are taking a thiazolidinedione will discontinue the medication for 10 weeks. At the start of the washout, each subject will be provided with diet and exercise counseling, a glucometer, a glycemic control diary in which to record daily fasting self-monitored blood glucose (SMBG) measurements and instructions regarding the appropriate circumstances under which a call to the clinic to register an observation of hyperglycemia should be made (see *Glycemic Control* below). Two weeks after the start of the washout period each subject will participate in a phone interview with study staff for SMBG data review and general safety evaluation. Subjects who remain

eligible at the end of the 6 or 10 week washout period will proceed to a 2-week placebo run-in period. Subjects will be ineligible if they exhibit fasting blood glucose values ≥ 250 mg/dL on two consecutive days during the wash-out period.

Eligible subjects who are treatment naïve will not require a washout period and will proceed to the run-in period. These subjects will be provided with diet and exercise counseling, a glucometer, and a glycemic control diary in which to record daily fasting SMBG measurements at the start of the 2-week placebo run-in period.

Treatment naïve subjects and subjects on background OHA who complete the washout will enter a 2-week single-blind placebo run-in period. Each subject will be provided with placebo run-in drug, dosing instructions, and instructions regarding the appropriate circumstances under which a call to the clinic to register an observation of hyperglycemia should be made (see *Glycemic Control* below). During the run-in, a placebo tablet should be taken daily in the morning prior to eating or drinking; the medication should be taken with water.

Subjects will not be eligible for randomization if during the run-in period they: 1) have fasting blood glucose values ≥ 250 mg/dL on two or more consecutive days, 2) omit more than one of the daily doses of placebo, 3) are deemed inappropriate for the study by the investigator, or 4) on day -3 to day -5 prior to randomization, have HbA1c value $< 7.0\%$ or $> 8.5\%$. The glycemic control requirement based on HbA1c values is outlined in Figure 1.

[figure not shown]

Figure 1. Glycemic Control Requirements Prior to Randomization

Approximately 320 eligible subjects will be randomized in equal ratio. Randomization will be stratified by the background anti-diabetes treatment status (treatment naïve or taking one OHA).

An assessment of bexagliflozin pharmacokinetics will also be conducted at 20 centers to include approximately 240 subjects. Samples will be taken during weeks 2, 6, or 12.

3.2.2 Treatment Period

The 12- week treatment period will start at randomization. At the start of the treatment period each subject will be provided with the investigational products, dosing instructions, and a glycemic control diary in which to record SMBG measurements. Information related to the occurrence of hyperglycemic or hypoglycemic events will be recorded. The investigational products will be orally administered in the morning prior to eating or drinking; the medication should be taken with water. Rescue medication for hyperglycemia will be allowed when deemed medically necessary by the investigator.

Each subject will be instructed to return to the clinic at weeks 2, 6, and 12 for safety and efficacy evaluations including review of adverse events and concomitant medications, vital signs, ECG, physical examination, and blood and urine specimen collections. On the day of the clinic visit a minimum fasting period of 10 hours (h) must be confirmed prior to blood draw.

Subjects will return to the clinic for a follow-up exit visit at week 14 or 2 weeks after the last dose of investigational product. Following the exit visit, subjects will be advised to see their primary physician to undergo treatment to control their diabetes. The duration of participation for each subject is up to 29 weeks based on the treatment status of each potential subject.

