3.2.3 Glycemic Control Monitoring

WASHOUT AND PLACEBO RUN-IN PERIODS

During the washout and placebo run-in period subjects will be instructed to determine SMBG daily after fasting overnight for a minimum of 10 h. If the fasting blood glucose is ≥ 250 mg/dL (13.9 mmol/L) the subject should contact the clinic within 24 h and the investigator will determine whether the participant should attempt to improve diet and exercise to maintain glycemic control or if the participant must withdraw from the study and initiate a more intense pharmacological regimen for glucose control. The participant will be excluded from further participation if fasting blood glucose values are ≥ 250 mg/dL prior to randomization on 2 or more consecutive days. Subjects with SMBG clinical signs or symptoms of hyperglycemia during the washout or run-in periods, including weight loss, blurred vision, increased thirst, increased urination, or fatigue should be excluded.

TREATMENT PERIOD

During the treatment period subjects will be advised to continue daily fasting SMBG measurements. Subjects should contact the clinic if any fasting SMBG is ≥ 270 mg/dL (15 mmol/L) from week 1 to week 6 or ≥ 240 mg/dL (13.3 mmol/L) from week 6 to week 12. Fasting blood glucose values collected via SMBG will be evaluated at study visits by the investigator. In addition, hyperglycemia will be monitored by FPG measurement at each study visit.

If hyperglycemia is identified through SMBG or FPG measurements, the investigator will determine whether the subject had fasted for a minimum of 10 h prior to the morning blood draw to ensure that the FPG value is truly a fasting sample. If proper fasting had not occurred, the subject will be asked to return for a repeat blood test within a week.

During the 12 weeks of the treatment period, hyperglycemia should be managed first with diet and exercise counseling and should be managed with changes in the medical therapy only if the investigator feels it is necessary for the well-being of the subject (see below, Prescription of Rescue Medication).

If a concomitant medication for hyperglycemia is to be prescribed, a sample must be drawn prior to the administration of the rescue medication so that a final HbA1c value can be ascribed to the latest date upon which the subject was taking investigational product as the sole therapy.

PRESCRIPTION OF RESCUE MEDICATION

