6.11 Concomitant Medication Assessments

A concomitant medication is any medication that the subject has been taking prior to enrollment and that the subject is expected to continue to take for some portion of the trial, as well as any medication other than the investigational product that the subject takes during the course of the trial.

The medications or treatment for controlling hypoglycemia must be recorded as concomitant medications in the CRF. Any medication given to treat hyperglycemia is considered a rescue therapy and should be recorded in the concomitant medication log.

Changes from baseline anti-hypertensive therapy and their rationale must be recorded in the CRF.

All prescription and over-the-counter medications, including vitamins and herbal supplements, that subjects receive during the trial must be documented on the CRF. This documentation should continue until the subjects complete the study.

Concomitant medications will be coded using the World Health Organization Drug Dictionary (WHO-DD). A table of concomitant medications based on the anatomic

therapeutic chemical classification (ATC) and preferred name will be produced. A listing of concomitant medications will include all medications taken by any subjects during the course of the study.

6.12 Removal of Patients from the Trial or Discontinuation of Investigational Product Administration

The investigator must emphasize to potential subjects the importance of continued participation for the full duration of the trial during the informed consent process. Potential subjects should be informed that the trial procedures will allow additional medications to control hyperglycemia or other adverse conditions. It is also important to emphasize that missing data and missed visits could affect the entire trial. If subjects are dissatisfied with the conduct of the trial but have not withdrawn, the investigator should make an effort to address their concerns and retain them in the trial if possible. In doing so, investigators must be careful that the efforts do not cross over into coercion. Investigator should encourage a subject to remain in the study even if the investigational product administration is stopped so that safety information can be collected.

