Participation in a clinical trial is voluntary. A subject can withdraw from the study at any time. The sponsor or investigator may terminate the study for medical or administrative reasons. If a decision is made to withdraw a subject from the study, no further investigational product should be administered. Even if the subject discontinues study medication, every attempt should be made to complete all required study evaluations and procedures. Reasons for all withdrawals should be recorded on the CRF. Examples of reasons for withdrawal include:

1. A protocol violation has occurred,
2. A serious or intolerable adverse event has occurred,
3. A clinically significant change in a laboratory parameter has occurred,
4. The sponsor or investigator terminates the study, or
5. The patient requests to be withdrawn from the study.

Subjects who do not complete the study but who have received investigational product should have a follow-up examination, including a physical examination, vital signs, ECG and clinical laboratory tests according to [Section 7](#).

Subjects who withdraw from the study will not be replaced.

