7.4 Exit Visit or Early Termination Visit

7.4.1 Visit V5 (week 14 or two weeks after the last dose of investigational product if a subject early terminates)

At the V5 visit the study investigator will:

- Review SMBG and glycemic control record
- Perform a complete physical examination including weight
- Measure vital signs, including blood pressures, pulse, temperature, and respiratory rate
- Perform a 12-lead ECG measurement
- Draw blood from subjects who have fasted a minimum of 10 h as described in [Section 6.7.2.1](#). The specific laboratory tests scheduled for this visit are listed in [Appendix 2](#)
- Collect clean-catch, mid-stream urine sample for urinalysis in all subjects and for UPT for women of child bearing potential
- Assess adverse events and record concomitant medications: If subjects have an ongoing serious adverse event, the subject should be followed until the adverse event is resolved or returns to baseline. All possible attempts should be made to document resolution of acute and chronic toxicities.

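### The plan does not say whether a subject who stops study drug but stays in the study attends the Week 12 visit, and the SAP can label an earlier off-drug HbA1c as Week 12

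*Protocol*

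**What the plan says.** Four places in the protocol bear on a subject who stops study drug early.

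- Section 3.2.2: "Subjects will return to the clinic for a follow-up exit visit at week 14 or 2 weeks after the last dose of investigational product". After that visit the subject is referred to a primary physician for diabetes care. The preceding paragraph of the same section has each subject return at Weeks 2, 6 and 12 for safety and efficacy, with no requirement to be on drug.
- Section 7.4.1 times V5 at "week 14 or two weeks after the last dose of investigational product if a subject early terminates". The term is not defined.
- Section 3.4 has subjects followed for two weeks after the last dose.
- Section 6.12: "Even if the subject discontinues study medication, every attempt should be made to complete all required study evaluations and procedures". It also asks the investigator to keep the subject in the study "even if the investigational product administration is stopped so that safety information can be collected". Of non-completers it says: "Subjects who do not complete the study but who have received investigational product should have a follow-up examination".

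For rescue, section 3.2.3 protects the last HbA1c on study drug alone: "a sample must be drawn prior to the administration of the rescue medication so that a final HbA1c value can be ascribed". There is no matching rule for stopping study drug.

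The SAP defines the primary variable as change to Week 12 (3.3.1) and removes only post-rescue values from the primary MMRM (3.8.1). It reports treatment completion and study completion separately (3.4.1). Section 3.1.9 maps an early-termination visit by the Table 2 windows. If the visit falls in no window, it goes to the next scheduled time point.

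**The concern.** A subject who stops drug but does not withdraw consent can be handled in two ways, and the text does not say which governs. Suppose the last dose is on Day 28. Counting from the last dose, the exit visit is on Day 42 and the subject then leaves. Under 6.12 the same subject goes on to V4 at Week 12. Such subjects are foreseen. Section 6.10.8 stops drug for hepatotoxicity without stating withdrawal from the study, whereas 6.10.3 states both for confirmed pregnancy.

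At stake is the primary endpoint in a dose-selection trial. Depending on how a site reads the protocol, the Week 12 HbA1c of an early stopper may be measured on schedule, be absent, or be an earlier off-drug value carrying the Week 12 label. A missing Week 12 value is also listed as a major deviation for the per-protocol set (SAP 3.2.1).

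**Working it through.** **1. The plan's own figure.** Inputs from Protocol 9.2: difference 0.5, SD 0.9, two-sided 5% t-test, 70 evaluable per arm. Noncentrality = 0.5 / (0.9 × √(2/70)) = 3.29 on 138 degrees of freedom, which gives power of 90.4%. The stated 90% is reproduced. Going from 70 to 80 per arm allows for a loss of (80 − 70)/80 = 12.5%. The protocol does not call this a drop-out rate, and the extra subjects also serve the safety evaluation.

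**2. What happens to an exit HbA1c.** Inputs from SAP 3.1.9, Table 2: Week 2 is Day 8-22, Week 6 is Day 36-50, Week 12 is Day 78-92, Week 14 is Day 93-105. Exit day = last-dose day + 14 (Protocol 3.2.2, ignoring the ±3-day visit window).

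| Last dose | Exit visit | SAP label for the exit HbA1c | Consequence |
|---|---|---|---|
| Day 1-8 | Day 15-22 | Week 2 | no Week 12 value |
| Day 9-21 | Day 23-35 | Week 6, by the next-time-point rule | no Week 12 value |
| Day 22-36 | Day 36-50 | Week 6 | no Week 12 value |
| Day 37-63 | Day 51-77 | Week 12, by the next-time-point rule | off drug 2 weeks, taken early |
| Day 64-78 | Day 78-92 | Week 12 | in window, off drug 2 weeks |
| Day 79-84 | Day 93-98 | Week 14 | V4 (Day 85) falls due before exit |

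In the fourth row the value is taken between 85 − 77 = 8 and 85 − 51 = 34 days before the nominal Week 12 day. From a last dose on Day 71 the exit falls on or after Day 85 (71 + 14), so V4 can be held before or with it. The early-exit reading therefore matters most for last doses before that.

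**3. What the choice of rule does to power (illustration only).** The documents give no rate of early stopping, so the rate is an assumption, taken from 5% to 25%. Two cases use the t-test of step 1. In the first, stoppers have no Week 12 value and the rest show the full effect. In the second, all 80 per arm are measured and stoppers keep no drug effect (worst case), so the mean difference is 0.5 × (1 − rate).

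| Assumed rate | Stoppers missing: n, power | All 80 followed: difference, power |
|---|---|---|
| 5% | 76, 92.5% | 0.475, 91.3% |
| 12.5% | 70, 90.4% | 0.4375, 86.3% |
| 25% | 60, 85.5% | 0.375, 74.5% |

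The two cases answer different questions about the drug. The choice between them should be written down, not left to sites.

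**The case against.** The best defence is that the documents, read together, already give the right answer. Section 3.2.2 has each subject return at Week 12 and nothing in it cancels V4. Section 7.5 uses early termination for subjects removed from the study or withdrawing consent, and SAP 3.1.9 ties the early-termination visit to subjects who withdraw early. Section 6.12 asks for all required evaluations, which include the V4 HbA1c, and warns that missing data and missed visits could affect the whole trial. On that reading the two-week clock applies only to those who leave.

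Most of this stands. It shows that early exit is one available reading, not the only one, so a reader who infers that V4 will never be held for early stoppers goes too far. What remains is that 3.2.2 lacks the qualifier found in 7.4.1, that 7.4.1 does not define its term, and that no sentence names V4 for a subject who is off drug.

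Two other inferences are tempting. One is that missing values favour the active arms because drug-related stopping rises with dose. That is plausible, but no figure in the documents shows unequal stopping, and off-drug values that are collected do enter the model. The other is to treat the allowance of 10 per arm, 40 of 320, as a count of Week 12 values at risk. The documents do not say how many subjects will stop drug and stay. Exits after a last dose on Day 37-78 do receive a Week 12 record. A subject followed to Week 12 may still have values excluded after rescue.

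**Conclusion.** The point holds as an ambiguity in data collection plus a mapping rule that can mislabel the result. It is not a certain loss of Week 12 data. On the early-exit reading, a last dose through Day 36 leaves no Week 12 HbA1c. A last dose on Day 37-63 yields a Week 12 label on a value taken 8 to 34 days early and two weeks off drug. A last dose on Day 64-78 yields an in-window value two weeks off drug. These ranges follow from the protocol's 14-day interval and SAP Table 2, and assume that the exit is held exactly on time and handled as an early-termination visit.

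The number of subjects cannot be stated. The sample size leaves room for at most 12.5% per arm, which is a planning allowance and not a forecast. Neither the direction nor the size of any bias between arms can be derived from the documents. The sample size calculation itself is correct. The matter is worth settling because it concerns the primary endpoint and the remedy is mainly wording.

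**What to change.** Reconcile Protocol 3.2.2, 3.4, 6.12 and 7.4.1 with SAP 3.1.9:

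- Define stopping study drug and leaving the study as separate events, and say which one early termination means.
- State that a subject who stops drug without withdrawing consent, and whom the protocol does not itself withdraw, continues scheduled HbA1c collection through Week 12 (V4).
- In 6.12, give efficacy as well as safety as the reason to stay.
- In SAP 3.1.9, do not label an early-termination HbA1c from outside Day 78-92 as Week 12.

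The post-dose visit carries safety examinations, and 3.4 ties follow-up to the last dose. Its timing, and all clinical management after drug is stopped, are for the sponsor to reconcile.

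The cost is small in conduct, since the visits are already scheduled for every randomised subject. The statistical cost is that some off-drug values enter the primary MMRM. The SAP already admits these, because it excludes only post-rescue data. They may dilute the estimated effect slightly; the worst-case column in the working shows how this grows with the assumed rate of stopping.
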